6.3. Exploratory Endpoints

6.3.1. Definition of Exploratory Endpoints

CCI [REDACTED]

[REDACTED]

[REDACTED]

[REDACTED]

[REDACTED]

[REDACTED]

6.3.2. Analysis Methods for Exploratory Endpoints

CCI [REDACTED]

[REDACTED]

[REDACTED]

[REDACTED]

[REDACTED]

6.3.2.1. Quality of Life Questionnaires SF-36

The Quality of Life Questionnaires SF-36 responses will be listed. The transformed scale scores (0 to 100 scale) and changes from baseline at each scheduled postbaseline visit will be presented

by treatment group for each of the 8 domains of the SF-36 (physical functioning, role-physical, bodily pain, general health, vitality, social functioning, role-emotional, and mental health), and for the physical component summary and mental component summary. Scoring of the SF-36 scales will be performed as described in Chapter 6 of the SF-36 Health Survey Manual and Interpretation Guide, Version 2 {Ware 2000}.

6.3.2.2. Chronic Liver Disease Questionnaire (CLDQ-HCV)

The Chronic Liver Disease Questionnaire (CLDQ-HCV) responses will be listed. The transformed scale scores (1 to 7 scale) and changes from baseline will be presented by study visit and treatment group for each of the four domains {Younossi 1999}:

- Activity/energy: question items 1, 3, 4, 5, 7, and 18
- Emotional function: question items 6, 8, 9, 11, 16, 23, 24, 27, and 28
- Worry: question items 14, 15, 17, 19, 20, 21, 22, and 29
- Systemic symptoms: question items 2, 10, 12, 13, 25, and 26.

The four domains will be calculated as an average of their non-missing constituent items (each domain score is calculated only if at least half of the corresponding items are not missing; otherwise, the domain score will be set as missing), and the overall CLDQ-HCV score will be the average of four domain scores. When all four domain scores are missing, the overall score will be set as missing as well.

6.3.2.3. Work Productivity and Activity Impairment Questionnaire: Hepatitis C (WPAI: Hepatitis C)

The Work Productivity and Activity Impairment Questionnaire: Hepatitis C (WPAI: Hepatitis C) results will be listed. Questions 5 and 6 will be transformed into a scale score from 0 to 10.

Current employment Yes/No ((item 1 on WPAI: Hepatitis C)) at different scheduled visits will be summarized using frequency and percentage. If the participant had a response of “Yes” to question 1, descriptive statistics (n, mean, SD, median, Q1, Q3, minimum, and maximum) for the percent of work time missed associated with hepatitis C ($P1=100 \times \text{Item2}/[\text{Item2}+\text{Item4}]$), percent of impairment while working due to hepatitis C ($P2=100 \times \text{Item5}/10$), and percent of overall work impairment due to hepatitis C ($P3=P1+P2 \times [1-P1/100]$) will be summarized for each scheduled visit. If P1 is not available, P3 will be set as missing as well.

For all participants, percent of daily activity impairment due to hepatitis C ($P4=100 \times \text{Item6}/10$) will be also calculated.

Change from baseline will be presented for all the percentages above.

6.4. Other Measurements

6.4.1. Limited Physical Exam

The limited physical exam includes height (at Day 1 only) and weight measurements for calculation of BMI. Assessments of ascites and encephalopathy will be conducted at each visit for calculation of CTP score. The results from the limited physical exam will be listed by participant ID and study visit.

6.4.2. Liver Imaging, Biopsy, Endoscopy and Transplant

Imaging of the liver will be performed as part of standard of care (e.g., CT, MRI, or Ultrasound results, if available). Liver biopsy will be performed at any time only if results available from biopsy performed as part of standard of care. An endoscopy will be performed to evaluate for varices at any time or at Day 1 (+/- 6 months) and within 6 months prior to Week 240 visit as in protocol. Liver transplant will be reported during the study.

A shift table of varices grade from endoscopy (no varices/small varices/large varices/unknown) from Day 1 to Week 240 will be provided by treatment group and baseline CTP class (CTP A, B, C, Unknown and total).

The results of all above will be listed by participant ID number and study visit. Results of endoscopy/imaging/biopsy collected at Day 1 visit but with a procedure date before or on the most recent HCV treatment end date will be flagged in the listing.

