### 6.1.1. Day 1 Assessments

For subjects enrolled from a Gilead parent protocol, a Day 1 visit will be scheduled within approximately 60 weeks from a subject's projected SVR 24 visit in the treatment protocol; or subjects may enroll from the GS-US-248-0122 SVR registry study at any time with Sponsor approval. For subjects who enroll after receiving an all-oral SOF-based regimen outside a clinical study, a Day 1 visit will be scheduled within approximately 2 years from the subject's SVR 12 date.

Subjects will be asked to come in fasting for this visit. The following will be performed and documented at Day 1:

- Obtain written informed consent (may be obtained prior to Day 1)
  - **CCI** [REDACTED]
- Review eligibility criteria
- Complete Health Related Quality of Life (HRQoL) Surveys
- Conduct limited physical exam
- Collect information for liver disease assessment. For subjects who enrolled having received an all-oral SOF-based regimen outside a clinical study, the liver disease assessment at screening will include a medical history of clinical liver-associated events and the start and stop dates of their most recent occurrences.
- Obtain blood samples (For subjects enrolling from the GS-US-248-0122 study, blood samples do not need to be collected for both studies if the ET from GS-US-248-0122 and D 1 visit from GS-US-337-1431 are done on the same day)
- Perform endoscopy (+/- 6 months, no need to repeat if subject has available endoscopy results performed within 6 months prior to Day 1 as standard of care)
- Perform transient elastography (+ 4 weeks, at sites with a Fibroscan®)
- Record any serious adverse events or adverse events that are related to protocol-required procedures occurring after signing of the consent form

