1.2. Registry Design

Design Configuration and Participant Population

GS-US-337-1431 is an observational study open to any cirrhotic participant with or without decompensated liver disease who have achieved SVR after receiving a SOF-based regimen

without IFN while participating in a Gilead-sponsored HCV study; or, at a subset of sites preselected by Gilead, who have previously received an all-oral SOF-based regimen outside a clinical study.

For participants enrolling from a Gilead parent protocol, the definitions of cirrhosis and of SVR are defined in the parent Gilead-sponsored treatment protocol. Participants who are enrolled after receiving an all-oral SOF-based regimen outside a clinical study, will have had cirrhosis confirmed prior to initiation of HCV treatment.

Once enrolled in the registry, participants will be followed for up to 5 years. For participants rolling over from a Gilead parent protocol, a Day 1 visit will be scheduled within approximately 60 weeks from a participant's projected SVR 24 visit in the parent protocol, or participants may enroll from the GS-US-248-0122 SVR registry study at any time with Sponsor approval. For participants who are enrolled after receiving an all-oral SOF-based regimen outside a clinical study, a Day 1 visit will be scheduled within approximately 2 years from the participant's SVR 12 date. Clinical visits will then occur every 24 weeks at Weeks 24, 48, 72, 96, 120, 144, 168, 192, 216, and 240.

Treatment Groups

This is a long-term observational follow-up registry study. No investigational medicinal product will be administered. The HCV regimen received in the parent studies will be used to assign treatment groups for analysis purposes. All the parent studies included in this registry are listed in Appendix 12.1.

Entry Eligibility Criteria

Participants must meet **all** of the following inclusion criteria to be eligible for participation in this study:

- 1) Willing and able to provide written informed consent;
- 2) Have previously participated in a Gilead-sponsored HCV study and received a SOF-containing regimen without IFN; OR

At pre-selected sites only, have received an all-oral SOF-based regimen outside a clinical study. These participants must have documentation of the regimen, start and end of treatment dates (month and year), and of having achieved SVR12;

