3.8. Visit Windows

3.8.1. Definition of Visits

Baseline Value will be the first non-missing value taken on or within 30 days of the registry start date (i.e., Day 1 Visit of the registry collected from the demographic eCRF). For questionnaire data, if no data are available within 30 days after the registry start date, the baseline value will be the last non-missing value prior to the registry start date.

Study days are calculated relative to registry start date as follows:

- For measurements that are collected before the registry start date: Visit date – registry start date.
- For measurement or events that are collected on or after the registry start date: Visit date – registry start date +1.

Last Day of the registry is the last recorded non-missing visit or collected data/assessment date in the database. When determining the last day of the registry, partial date will be imputed as 01 if only day is missing and 01 January if day and month are missing.

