3.8.2. Analysis Windows

Participant visits might not occur on protocol-specified visit days. Therefore, for the purpose of analysis, observations (corresponding laboratory test or quality of life questionnaires) will be assigned to analysis windows. Windows will be constructed so that the boundaries of windows are the midpoint between consecutive protocol-specified visit days. The analysis windows for liver disease assessment, laboratory data, Model for End-Stage Liver Disease (MELD) score and data from quality of life survey Short Form-36 (SF-36) are defined in [Table 3-1](#). The analysis windows for transient elastography (Fibroscan score) are defined in [Table 3-2](#). Endoscopy will be assigned to either Day 1 or Week 240 with +/- 6 months based on the test performed date as shown in [Table 3-3](#).

Table 3-1. Analysis Windows for Liver Disease Assessment, Laboratory Data, CTP/MELD Score and Quality of Life Surveys

Analysis Visit ID	Nominal Day	Lower Limit	Upper Limit
Baseline ^a	1	1	30
Baseline ^b	1	(none)	30
Week 24	168	31	252
Week 48	336	253	420
Week 72	504	421	588
Week 96	672	589	756
Week 120	840	757	924
Week 144	1008	925	1092
Week 168	1176	1093	1260
Week 192	1344	1261	1428
Week 216	1512	1429	1596
Week 240	1680	1597	>=1680

a Baseline window for laboratory tests, liver disease assessment and CTP/MELD score only.

b Baseline window for Quality of Life Surveys only.

Table 3-2. Analysis Windows for Transient Elastography (Fibroscan Score)

Analysis Visit ID	Nominal Day	Lower Limit	Upper Limit
Baseline	1	-75	168
Week 48	336	169	504
Week 96	672	505	840
Week 144	1008	841	1176
Week 192	1344	1177	1512
Week 240	1680	1513	>=1680

Table 3-3. Analysis Windows for Endoscopy

Analysis Visit ID	Nominal Day	Lower Limit	Upper Limit
Day 1	1	-182 (about -6 months)	182 (about 6 months)
Week 240	1680	1513 (about 6 months prior/Week 216)	>=1680
Others*	-	-	-

* For endoscopy performed to evaluate for varices at time other than the two protocol-defined visits, the test result will be assigned to the closest protocol scheduled liver disease assessment visit.

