6.4.3. Transient Elastography

A transient elastography will be performed to assess the liver elasticity at Day 1 (+ 4 weeks) and every 48 weeks (+/- 4 weeks) through Week 240 at sites with a Fibroscan® or comparable equipment. Descriptive statistics (n, mean, SD, median, Q1, Q3, minimum, and maximum) will be provided by visit and by treatment group as follows:

- Baseline values
- Values at each postbaseline visit
- Change from baseline at each postbaseline visit

Analysis visit windows as defined in Section 3.8.2. Data record with a procedure date prior to the most recent HCV treatment end date will be excluded in the above summary table. In the case of multiple values in an analysis window, data will be selected for analysis as described in Section 3.8.3.

The results of the transient elastography including the reported interquartile range will be listed by participant ID number and visit. Data record with a procedure date prior to the most recent HCV treatment end date will be flagged.

The shift table for fibroscan category by treatment group will be provided based on following:

- Category F0 to F2: 9.5 kPa or less
- Category F3: 9.6 to 12.5 kPa
- Category F4: greater than 12.5 kPa

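### SAP 6.4.2 states no exclusion from the varices shift table for Day 1 endoscopies dated on or before the end of HCV treatment, although Table 3-3 can admit them

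*SAP*

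**What the plan says.** SAP 3.8.2, Table 3-3, gives the Day 1 endoscopy window as study day -182 to day 182. This follows Protocol 6.1.1, under which there is "no need to repeat if subject has available endoscopy results performed within 6 months prior to Day 1 as standard of care". A table footnote covers endoscopies done at other times: "the test result will be assigned to the closest protocol scheduled liver disease assessment visit".

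SAP 6.4.2 plans a shift table of varices grade from Day 1 to Week 240, by treatment group and by baseline CTP class. The same section says that endoscopy, imaging and biopsy results collected at the Day 1 visit "with a procedure date before or on the most recent HCV treatment end date will be flagged in the listing". It gives no other handling for them. Neither the data conventions in SAP 3.7 nor the record selection rules in 3.8.3 add an exclusion.

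SAP 6.4.3, on transient elastography, goes further: "Data record with a procedure date prior to the most recent HCV treatment end date will be excluded in the above summary table". These records are also flagged in the listing.

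**The concern.** The primary objective in both documents is progression or regression of liver disease following SVR. Protocol 8.6.2 names varices among the clinical signs to be summarised for it. Scheduled endoscopy takes place only at Day 1 and near Week 240, and the shift table is the only summary of varices grade that the SAP specifies.

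If the Day 1 grade comes from an endoscopy done during or before treatment, the shift to Week 240 includes any change that took place on treatment or between treatment end and registry start. The table would still present that as change over the registry period. The SAP recognises such records and removes their elastography counterparts from one summary, so the silence on the varices table looks like an omission.

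**Working it through.** **Inputs**

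- Lower limit of the Day 1 endoscopy window: day -182 (SAP Table 3-3). SAP 3.8.1 sets the convention: "For measurements that are collected before the registry start date: Visit date – registry start date". Day -182 is therefore 182 days, or 26 weeks, before registry start.
- SVR12: about 12 weeks after the last dose (inclusion criterion 3), taken as 84 days.
- SVR24: taken as 24 weeks, or 168 days, after the last dose. This is an assumption, since the parent protocols are not part of these documents.
- Rollover entry (SAP 1.2): "a Day 1 visit will be scheduled within approximately 60 weeks from a participant's projected SVR 24 visit in the parent protocol". The upper end is 60 × 7 = 420 days after SVR24.
- Commercial entry (SAP 1.2): "a Day 1 visit will be scheduled within approximately 2 years from the participant's SVR 12 date". The upper end is about 730 days after SVR12.
- Neither route has a stated minimum gap. The earliest entry is taken as the SVR12 date (commercial) and the SVR24 date (rollover).

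The plan gives no figure of its own to reproduce.

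**Formula.** Let G be the number of days from treatment end to Day 1. The window opens G − 182 days after treatment end, so it reaches back before treatment end when G < 182.

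| Entry | G (days) | Window opens, relative to treatment end |
|---|---|---|
| Commercial, on the SVR12 date | 84 | 84 − 182 = −98 |
| Commercial, SVR12 + 98 days | 182 | 0 |
| Commercial, latest | 84 + 730 = 814 | +632 |
| Rollover, on the SVR24 date | 168 | 168 − 182 = −14 |
| Rollover, SVR24 + 14 days | 182 | 0 |
| Rollover, latest | 168 + 420 = 588 | +406 |

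The overlap exists only at the early end of each entry range.

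**Rough scale, under an assumption.** If entry were uniform over the permitted range, the window would reach before treatment end for 98/730 = 13% of commercial entries and 14/420 = 3% of rollover entries. The documents give no entry distribution. These are shares of entries whose window reaches that far; the share with an endoscopy actually dated there would be smaller.

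**Elastography.** Its baseline window opens at day -75 (Table 3-2). With entry on the SVR12 date it opens 84 − 75 = 9 days after treatment end. The stated exclusion thus applies to the measure with the smaller exposure.

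**Record selection.** SAP 3.8.3 takes the record closest to the nominal day, so an early endoscopy counts only if no other lies closer. That protects less than it might, because the protocol does not require a repeat when a standard-of-care result is available. The early record may be the only one.

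**The two sections side by side**

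| | Endoscopy (6.4.2) | Elastography (6.4.3) |
|---|---|---|
| Flag in listing | Yes | Yes |
| Excluded from descriptive summary | No such summary planned | Yes |
| Exclusion stated for shift table | No | No |
| Date boundary | On or before treatment end | Before treatment end |

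**The case against.** The strongest defence is that the protocol itself accepts a standard-of-care endoscopy from the previous 6 months, while the Day 1 elastography has only a forward window of 4 weeks. An early endoscopy can be fully compliant, and excluding it removes the baseline of a participant who was told that no repeat was needed. Flagging is then a defensible choice. This stands as an argument about cost. It does not make a pre-treatment-end grade a measure of status following SVR.

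Timing also limits the problem. The overlap needs early entry, and the procedures table in SAP Appendix 12.2 puts Day 1 at about 48 weeks from the final treatment-protocol visit. Even counted from treatment end, that is 336 days, so the window would open 336 − 182 = 154 days after treatment end. SAP 5.1 does plan a category for a gap of less than 6 months between treatment end and registry start. The formula printed beside it counts from the last day of the parent study, however, so it does not size the overlap. Overlap remains possible under SAP 1.2, and 6.4.2 provides for such records.

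Four stronger readings are tempting, and the documents do not support them.

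- A reader might infer that the SAP treats the two shift tables differently. The exclusion in 6.4.3 refers to the descriptive table above it; none is stated for the Fibroscan shift table that follows.
- A reader might infer that the Table 3-3 footnote lets an endoscopy of any age become the Day 1 value. For a procedure before registry start the closest scheduled visit is Day 1, but the table puts these records in a separate Others row, and nothing says that they fill the Day 1 column. Protocol 6.3.5 also limits what is asked for at Day 1 to the period since the last parent-protocol visit or since the end of HCV therapy. The footnote is ambiguous and worth closing.
- A reader might infer that 6.4.2 says flagged records stay in the shift table. It is silent. They stay because nothing removes them.
- A reader might infer that a primary estimate is affected. The table belongs to SAP 6.4, Other Measurements. The progression events in 6.1.3.2.1 include bleeding varices but not varices grade, so the Kaplan-Meier analyses do not change.

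**Conclusion.** The point holds as a limited one. Followed as written, the plan can place a varices grade from on or before treatment end in the Day 1 column of a table meant to show change following SVR. This requires Day 1 less than 182 days after treatment end and no endoscopy closer to Day 1. The largest overlap is 98 days for commercial entry on the SVR12 date and 14 days for rollover entry on the SVR24 date. It is gone once Day 1 is 98 days after SVR12 or 14 days after SVR24, respectively.

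These figures rest on 84 and 168 days for SVR12 and SVR24 and on entry no earlier than those dates. The number of participants affected is not stated, and no percentage of shift-table rows can be derived from the documents. The output is supportive and no hypothesis is tested. The change is worth making because it is cheap, and because the SAP already applies the principle to its elastography summary.

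**What to change.** Three sentences in the SAP, or a documented change in the CSR, which SAP Section 1 allows after finalisation:

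1. In 6.4.2, exclude endoscopy records dated on or before the most recent HCV treatment end date from the Day 1 column of the varices shift table and keep them in the flagged listing. Alternatively, present the table with and without them.
2. In 6.4.3, state the same exclusion for the Fibroscan shift table, and use one date boundary in both sections.
3. In the Table 3-3 footnote, state that Others endoscopies before day -182 are listed only and do not fill the Day 1 column.

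The endoscopy flag is already planned, so programming is small. The cost is that some participants lose a baseline varices grade and drop out of the shift table; showing both versions makes that loss visible. The exclusion does not remove endoscopies done after treatment end but before SVR12 was reached, so a table footnote should say that the Day 1 grade may come from that interval.

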6.4.3. Transient Elastography

A transient elastography will be performed to assess the liver elasticity at Day 1 (+ 4 weeks) and every 48 weeks (+/- 4 weeks) through Week 240 at sites with a Fibroscan® or comparable equipment. Descriptive statistics (n, mean, SD, median, Q1, Q3, minimum, and maximum) will be provided by visit and by treatment group as follows:

- Baseline values
- Values at each postbaseline visit
- Change from baseline at each postbaseline visit

Analysis visit windows as defined in Section 3.8.2. Data record with a procedure date prior to the most recent HCV treatment end date will be excluded in the above summary table. In the case of multiple values in an analysis window, data will be selected for analysis as described in Section 3.8.3.

The results of the transient elastography including the reported interquartile range will be listed by participant ID number and visit. Data record with a procedure date prior to the most recent HCV treatment end date will be flagged.

The shift table for fibroscan category by treatment group will be provided based on following:

- Category F0 to F2: 9.5 kPa or less
- Category F3: 9.6 to 12.5 kPa
- Category F4: greater than 12.5 kPa

6.5. Changes from Protocol-Specified Endpoint Analyses

No change from protocol-specified endpoint analysis is planned.

7. SAFETY ANALYSES

Analysis of safety measures will be descriptive and will include participants in the Safety Analysis Set. All safety data collected on or after the date of enrollment through the remainder of the study will be included.

As there was no intervention in this study, only AEs related to the required procedures by this registry were recorded. Any reference to an AE or serious adverse event (SAE) in this SAP will be referring to AEs and SAEs related to procedures required by this registry. All deaths, regardless of relatedness to study procedures were recorded when available. The immediate cause and date of death were collected when available.

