6.1.3.2. Proportion of Participants Who Develop Liver Disease Progression or Regression

6.1.3.2.1. Liver Disease Assessment Including Hepatocellular Carcinoma

Events related to liver disease progression include:

- Hepatic encephalopathy
- Hepatocellular carcinoma (HCC)
- Hepatorenal syndrome
- Hepatopulmonary syndrome
- Portopulmonary hypertension
- Hepatic hydrothorax
- Bleeding varices
- Spontaneous bacterial peritonitis
- Liver Transplant
- Ascites
- Liver-related death

Hepatic decompensation events include:

- Hepatorenal syndrome

- Hepatopulmonary syndrome
- Portopulmonary hypertension
- Hepatic hydrothorax
- Hepatic encephalopathy
- Bleeding varices
- Spontaneous bacterial peritonitis
- Ascites
- Liver-related death

Except for ascites (using data collected from liver imaging)/liver transplant/death, other events will be all collected from liver disease assessment page in eCRF. Minimal or trace ascites will not be treated as a liver event. Liver-related death will be identified by Clinical Research based on the immediate cause of death.

Participants with events related to liver disease progression that were identified prior to registry start date will be excluded from the analysis but will be listed.

Participants with De Novo HCC since registry start are defined as participants who were not identified with HCC prior to registry start and only had HCC since registry start.

Summary of participants with liver events will be provided, including the percentage of participants with events among FAS, the percentage of participants for each type of events among all the participants with events, and the percentage of participants with any event prior to registry start among FAS.

Person-time pertaining to KM analysis of time to events in this section will be calculated as: first event date (for participants who experienced events) or last day of registry (for participants who did not experience events) – registry start date + 1.

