For time to first liver event since registry start, KM estimate of the proportion of participants with events related to liver disease progression, the cumulative number of participants who experienced events, were at risk, and had been censored will be summarized by treatment group and time point (Week 0, 24, 48,..., 216, and 240), where Week 0 to 216 are the exact weeks elapsed since registry start date (i.e., 0, 168, 336,..., and 1512 days), and Week 240 includes 1680 days elapsed since registry start date plus additional 30 days (i.e. 1710 days). Participants with liver events prior to registry start will be excluded from this analysis.

Same summary table as above will be provided separately for participants with De Novo HCC, with hepatic decompensation events, with liver transplant, and with all-cause death.

Same summary tables will be provided for above endpoints by baseline CTP class (CTP A, B, C, Unknown and total). Time to the first liver event and time to De Novo HCC since registry start will be summarized descriptively (n, mean, SD, median, Q1, Q3, minimum, and maximum) in a table for those participants with events occurring only during the registry study.

The KM plots will also be presented in a figure.

A by-participant, by visit listing of participants who developed above events will be provided by participant ID number in ascending order (events prior to registry start will be flagged). A separate listing will be provided for participants with De Novo HCC since registry start. Participants who experienced an HCC event more than 30 days after 240 weeks elapsed since registry start date (i.e. > 1710 days)/participants with HCC prior to registry start date will be listed separately.

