7.1.4. Summaries of Adverse Events and Deaths

A brief high-level summary of study procedure related AEs will be provided by treatment group and overall, including the number and percentage of participants who experienced at least 1 AE in the following categories: any AE, any AE of Grade 2 or above, any AE of Grade 3 or above, any SAE, and AE leading to premature discontinuation of study. All deaths (including those that are procedure related and those that are not procedure related) observed during the study will also be summarized and included in this table.

AE summaries will provide the number and percentage of participants for reported AEs by treatment group and by SOC and PT based on the Safety Analysis Set as follows:

- All AEs
- All AEs with Grade 3 or above
- All AEs by grade
- All SAEs
- AEs leading to premature discontinuation of this registry study

Multiple events will be counted only once per participant in each summary. Adverse events will be summarized and listed first in alphabetic order of SOC (and HLT within each SOC if applicable), and then by PT in descending order of total frequency within each SOC. For summaries by severity grade, the most severe grade will be used for those AEs that occurred more than once in an individual participant during the study.

In addition to the above summary tables, all AEs, all AEs by grade will be summarized by treatment group and by PT only, in descending order of total frequency.

By-participant listings will be provided by participant ID number in ascending order for the following:

- All AEs
- AEs of Grade 3 or above
- SAEs
- All deaths (with a flag indicating liver-related death identified by Clinical Research)
- All AEs leading to premature discontinuation of this registry study

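### The mortality Kaplan-Meier (KM) rule has no cut-off at a participant's own exit: recorded deaths count on their date, everyone else is censored at the last registry date

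*SAP*

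**What the plan says.** **Recording of deaths.** SAP 7 states: "All deaths, regardless of relatedness to study procedures were recorded when available". It adds: "The immediate cause and date of death were collected when available". The limit on safety data is set for the study, not the participant: "All safety data collected on or after the date of enrollment through the remainder of the study will be included". The summary table in SAP 7.1.4 covers "All deaths (including those that are procedure related and those that are not procedure related) observed during the study".

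**Person-time.** SAP 6.1.3.2.1 ends each participant's time at "first event date (for participants who experienced events) or last day of registry (for participants who did not experience events". SAP 3.8.1 defines the censoring date: "Last Day of the registry is the last recorded non-missing visit or collected data/assessment date in the database".

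**Where the rule applies.** SAP 6.1.3.2.1 repeats the KM table for participants "with hepatic decompensation events, with liver transplant, and with all-cause death", by treatment group and by baseline CTP class. Liver-related death is also a component of the liver-progression and hepatic-decompensation endpoints. Progression belongs to a primary endpoint (SAP 6.1.1).

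**Exit.** Transplant, confirmed virologic relapse or re-infection, and withdrawal of consent all end participation (protocol 3.2). The last planned contact is the Early Termination visit (protocol 6.2.4), and no later vital-status check is described. Protocol 8.6.1 specifies KM estimates for progression in which early discontinuation leads to censoring.

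**The concern.** Take two participants who leave at Week 96 and of whom nothing further is recorded, except that one is later reported to have died at Week 200. That one contributes 200 weeks and an event. The other, alive at Week 200, contributes 96 weeks and no event. After exit, a recorded death brings a participant back into the risk set, while survival ordinarily does not. KM estimation assumes that the length of observation does not depend on the outcome in this way.

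At stake is the all-cause mortality curve and, through liver-related death, part of the progression and decompensation curves. The size of the effect would depend on how often sites happen to hear of a death. If that differed between treatment groups or CTP classes, the displayed columns would not be comparable, but the documents do not show whether it does.

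**Working it through.** The plan states no mortality estimate, event count or sample size, so it has no figure of its own to reproduce.

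**1. Text check**

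- SAP 6.1.3.2.1 ends the KM table at 240 × 7 + 30 = 1,710 days. That bounds the table but is not a cut-off at exit.
- SAP 3.7 moves an imputed partial death date forward to the last visit when it falls earlier. It sets no upper limit.
- For virologic failure, SAP 6.1.3.1 says in terms that those who leave early are censored. SAP 6.1.3.2.1 has no matching sentence for liver events or death, and SAP 6.5 declares no change from the protocol analyses.
- Virologic failures and hepatocellular carcinoma (HCC) events after day 1710 are listed separately. No such rule is given for deaths.

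**2. Inputs for size**

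- Five-year survival of 91% (compensated cirrhosis) and 50% (decompensated), from protocol 1.2. These are background rates, not registry data.
- Dropout of 5% or 10% per year: assumed.
- Share q of post-exit deaths that are recorded: assumed, 0 to 1.

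**3. True mortality at day 1710 (1710 / 365.25 = 4.68 years)**

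- 91% survival: hazard = −ln(0.91)/5 = 0.0189 per year; 1 − exp(−0.0189 × 4.68) = 8.5%.
- 50% survival: hazard = −ln(0.50)/5 = 0.139 per year; 1 − exp(−0.139 × 4.68) = 47.7%.

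**4. Exit unrelated to prognosis**

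Simulation of 400,000 participants per setting, with exponential death and dropout times and KM read at day 1710. Under the SAP rule, all pre-exit deaths and a share q of post-exit deaths count on their dates, and all others are censored at exit.

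| Dropout per year | q | 91% survival: SAP rule (true 8.5%) | 50% survival: SAP rule (true 47.7%) |
|---|---|---|---|
| 5% | 0.5 | 9.0% (+6%) | 49.4% |
| 10% | 0.5 | 9.5% (+12%) | 51.5% |
| 10% | 1 | 10.7% (+26%) | 54.9% |

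Relative error: 9.0/8.5 = 1.06; 9.5/8.5 = 1.12; 10.7/8.5 = 1.26. Censoring everyone at exit returns 8.4% to 8.5% and 47.6% to 47.7%. At q = 0 the SAP rule gives the same result and there is no bias.

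An alternative set of assumptions, 10% to 40% withdrawn by day 1710 and q from 0.25 to 1, gives ratios to the truth of 1.01 to 1.28 at 91% survival.

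**5. Exit related to prognosis**

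91% survival before exit, 30% withdrawn by day 1710, death hazard three times higher after exit (assumed). True mortality is about 10.8% to 10.9%.

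| q | SAP rule | Ratio to truth |
|---|---|---|
| 0 (same as censoring at exit) | 8.5% | 0.78 |
| 0.25 | 9.5% | 0.88 |
| 0.5 | 10.6% | 0.98 |
| 1 | 12.7% | 1.17 |

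At 10% dropout per year with the same threefold hazard and q = 0.5, the SAP rule gives about 11.5% against a true 11.6%, and censoring at exit gives 8.4%. Across hazards two to five times higher and 20% to 30% withdrawn, the ratio runs from 0.65–0.92 at q = 0 to 1.09–1.18 at q = 1.

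In every setting with q above 0, the SAP estimate lies above KM censored at exit. Whether it lies above the truth depends on who leaves and on q.

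**The case against.** **The premise may be empty.** The documents do not say that any post-exit death was recorded. Follow-up is planned to early termination or completion, and no later survival contact is described. Recording when available may simply mean that data are incomplete. With no post-exit deaths there is no bias. This stands: the defect is a gap in the rule, not a demonstrated error in the results. But no text excludes such deaths, and the limits in SAP 7 and 7.1.4 refer to the study rather than to the participant's exit.

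**Inflation is not established.** A reader might infer that reported mortality will be too high. That holds only if exit is unrelated to prognosis or capture is high. Transplant forces exit, so some exits plausibly relate to prognosis, and step 5 shows that the net error can then be downward. For the same reason, closing at exit can understate mortality by more than the SAP rule does. This stands and shapes the fix.

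**There are some limits on follow-up.** A reader might infer that deaths count without end. The KM tables stop at day 1710. The last-registry-day definition also takes in any collected data, so a recorded later contact would extend a survivor's time too. This stands, although no such contact is planned.

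**The reach is limited.** All-cause death is not a listed primary or secondary endpoint, the study is descriptive, and all deaths are listed. In the composites, liver-related death is one of 11 components (progression) or 9 (decompensation) and counts only when it is the first event. Participants with pre-registry liver events are excluded from the progression analysis. The all-cause percentages therefore cannot be carried over to those endpoints. The KM tables are also not split by country, so a distortion between countries cannot be read from them.

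**Conclusion.** The concern holds in conditional form. As written, the rule treats recorded deaths and survivors differently after exit, and nothing closes death follow-up at the participant's own exit. If any post-exit deaths are recorded, the estimate exceeds KM censored at exit.

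For all-cause death with exit unrelated to prognosis, the relative overstatement is about +6% to +26% at assumed dropout of 5% to 10% per year, 50% to 100% capture and 91% five-year survival. It is zero with no capture. With sicker participants leaving and incomplete capture, the net error may be small or downward. The documents do not support an unconditional claim that mortality is inflated, nor any figure for the progression or decompensation endpoints.

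Dropout, capture and the higher post-exit hazard are assumptions, and the survival rates are for cirrhosis generally rather than for this cohort after sustained virologic response. The remedy is cheap and brings the SAP into line with protocol 8.6.1.

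**What to change.** In SAP 6.1.3.2.1, apply one closing rule to deaths and survivors, for all-cause death and for the liver-related death component:

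- Censor at the earlier of the completion or discontinuation date and day 1710.
- Count a death only if it occurs by that point, or if it is itself the reason participation ended and falls by day 1710.
- List later deaths separately, as the SAP already does for HCC and virologic failure after day 1710.
- Because closing at exit can understate mortality when exit relates to prognosis, also report the KM estimate with all known deaths as a sensitivity analysis.
- State the number of post-exit deaths by treatment group and CTP class, so that readers can judge how far the two estimates could differ.
- Say how a death with no date at all is handled. SAP 3.7 covers only partial dates.

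The cost is a short SAP change and one derivation from disposition data already planned for summary in SAP 4.1, plus one repeat of the KM table. The downside is that known late deaths leave the main KM estimate. They remain in the sensitivity analysis and the death listing.
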